A linear model will be fit (for all of the data or for a subset of histopathology values, depending on the findings from the plot) where the dependent variable is the vascuCAP™ measurement ( $X$ ) and the independent variable is the histopathology value ( $Y$ ). Generalized estimating equations (GEEs) (to account for the fact that some patients will have more than one target lesion) will be used to estimate the linear function:  $E(Y|X) = \beta_0 + \beta_1 X$ . An unstructured working covariance will be used. We will construct a 95% CI for the intercept  $\beta_0$  using a t-statistic as the pivotal statistic. CIs not containing 0 indicate fixed bias. We will also construct a 95% CI for the slope  $\beta_1$ . CIs not containing 1 indicate proportional bias [11].

The precision of the vascuCAP™ measurements will be estimated by the standard deviation:

$$\sqrt{\frac{1}{n-1} \sum_{i=1}^n (Y_i - X_i - \bar{d})^2} \text{ where } \bar{d} \text{ is the sample mean of the differences, } \bar{d} = \frac{1}{n} \sum_{i=1}^n (Y_i - X_i) \text{ [1].}$$

We will construct a 95% CI for the precision using bootstrap methods.

We will plot the bias profile (plot of bias of measurements for various ranges of histopathology values vs. the histopathology value) and precision profile (plot of standard deviation of vascuCAP™ measurements from patients with similar histopathology values vs. the histopathology value) as visual summaries of vascuCAP™ performance for the bias and precision components, respectively [12].

In addition to reporting these technical performance characteristics of the volume measurements, we will also report i) the coverage probability (CP) and ii) a discrimination index [11]. The CP is the probability that the absolute difference between the value measured by vascuCAP™ and the value measured by histology is less than  $d_0$ , i.e.  $\pi = \Pr(|Y - X| < d_0)$ . We will plot the CP for a range of values for  $d_0$ . The discrimination ability of the measurements, i.e. the ability of vascuCAP™ to discriminate between different magnitudes of histopathology values, will be measured using the area under the ROC curve for continuous measures [13]. 95% CIs for the CP and ROC area will be constructed using methods for clustered binary data [14] and clustered ROC data [15], respectively.

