The volume measurements are considered the most critical because they will be used to construct a score to predict rupture risk. Thus, we considered the width of 95% confidence intervals for the bias and the between-subject variance as a function of sample size (see Tables 1 and 2). The following assumptions were made: 1) the volume measurements are normally distributed; 2) carotid artery patients contribute one target lesion each, while PAD patients contribute two target lesions each; 3) target lesions from the same patient are moderately correlated ( $r=0.5$ ); 4) one-quarter of all patients will be PAD patients; 5) results from femoral and carotid target lesions can be pooled; 6) the average volume of an analyte is  $25\text{mm}^3$ ; and 6) the precision of the vascuCAP™ measurements is 10-20% of the volume of analyte.

From Table 4, if the SD was 15% of the mean volume, then we expect to be able to construct a 95% CI for the bias of total width of 10% with  $n=35$ . If the SD was 20%, then with  $n=35$  we expect to construct a 95% CI of total width of 14%. Similarly, from Table 5, if the SD was 15% of the mean volume, then with  $n=35$  we expect to be able to construct a 95% CI for the precision of total length 8%; if the SD was 20%, then we expect to be able to construct a 95% CI for the precision of total length 11%. We plan to recruit 75 patients (55 carotid artery patients and 20 PAD patients) in phase one to account for the fact that the estimates of bias and

precision may need to be reported in strata based on the magnitude of the histopathology volume and/or by anatomic location. In phase two we plan to recruit at least the minimum of 35 (25 carotid artery patients and 10 PAD patients) and possibly more depending on the results of the training set.

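### Aim I sample size: Table 5 does not follow its own formula, Table 4 sizes a bias interval that the analysis does not plan, and the bias regression is written in two directions

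*Combined protocol and SAP*

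**What the plan says.** All of this is in section 8.1 (Aim I) of the combined protocol and SAP.

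- **Analysis.** A GEE regression links the vascuCAP and histopathology volumes. A 95% CI is planned for the intercept ("CIs not containing 0 indicate fixed bias") and for the slope ("CIs not containing 1 indicate proportional bias"). The text labels vascuCAP X and makes it the dependent variable, "and the independent variable is the histopathology value" (labelled Y), and then writes E(Y|X) = β0 + β1X. The quantity d-bar, which "is the sample mean of the differences", enters only through the SD formula for precision. That SD has a bootstrap CI; d-bar has none.
- **Sample size.** Table 4 gives the half-width of a CI for bias as t(m−1)·SD/√m. Table 5 gives a chi-square CI for the SD on m−1 degrees of freedom. Both use the effective sample size m.
- **Widths at n=35.** For bias at SD 15%: "we expect to be able to construct a 95% CI for the bias of total width of 10" per cent. At SD 20%: "we expect to construct a 95% CI of total width of 14" per cent. For precision at SD 15%: "we expect to be able to construct a 95% CI for the precision of total length 8" per cent. At SD 20%: "we expect to be able to construct a 95% CI for the precision of total length 11" per cent.
- **Use.** These widths support the minimum of 35 patients in phase two, the data set meant for the 510(k). Section 4 leaves any larger number to be set after phase one.

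**The concern.** The widths are the quantitative support the plan offers for n=35, so a reader should be able to reproduce them and match each to an analysis that will be done.

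Table 4's formula is the interval of a mean difference, yet the rules that declare fixed and proportional bias use the intercept and slope. Someone told that 35 patients give a bias interval 10% wide could take that as the precision of the fixed-bias test, and the plan does not say so or show it. The contradiction in regression direction matters because the two regressions have different slopes even for an unbiased device, and the decision rule compares the slope with 1. Table 5 matters less: it feeds no acceptance threshold, but the text quotes it as support.

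**Working it through.** **Inputs from section 8.1:** mean volume 25 mm³; SD of the difference 2.5, 3.75 or 5.0 mm³ (10%, 15%, 20%); one quarter of patients contribute two lesions with correlation 0.5; 95% confidence. The footnotes give m = (3/4)n + (1/4)n·(2/1.5) = 1.0833n, so n=35 gives m = 37.92.

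**Table 4 and the bias widths.** All 18 printed entries agree with the footnote within 1.4%. At n=35:

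- SD 3.75: 2 × 2.026 × 3.75/√37.92 = 2.47 mm³, or 9.9% of 25 (quoted 10%).
- SD 5.0: 2 × 2.026 × 5.0/√37.92 = 3.29 mm³, or 13.2% (quoted 14%).

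**Table 5.** The footnote gives SD·√((m−1)/χ²) with m−1 df at both limits. None of the 18 intervals reproduces. Examples for SD 2.5:

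| n | m | By footnote | Printed | Excess length |
|---|---|---|---|---|
| 10 | 10.83 | [1.74, 4.41] | [1.80, 4.77] | 11% |
| 30 | 32.50 | [2.01, 3.32] | [2.08, 3.51] | 9% |
| 60 | 65.00 | [2.13, 3.02] | [2.19, 3.14] | 7% |

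Over the whole table the excess is about 6-11%. Every printed limit is recovered within 0.015 by keeping m−1 in the numerator and using smaller chi-square df (9, 19, 29, 40, 50, 60). That fits a mix of two df, but the cause is an inference.

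At n=35 by footnote:

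- SD 3.75: [3.06, 4.85], length 1.80 mm³, or 7.2% (quoted 8%).
- SD 5.0: [4.08, 6.47], length 2.40 mm³, or 9.6% (quoted 11%).

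**Width of the intercept CI.** This needs the SD of histopathology volume (SDref) and the true slope, neither of which the plan gives. I assume a range of CV = SDref/25. For vascuCAP regressed on histopathology, the total width as a share of the mean is

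2·t(m−2)·s·√(1/m + 25²/((m−1)·SDref²))/25, with s² = SD² − (1−slope)²·SDref².

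At slope 1, s = SD. For CV 100% and SD 3.75: 2 × 2.028 × 3.75 × √(0.02637 + 0.02709)/25 = 14.1%. Across the range, at SD 15%:

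| Assumed CV | Intercept width, slope 1 | Table 4 quantity | Slope CI total width |
|---|---|---|---|
| 150% | 11.9% | 9.9% | 0.07 |
| 100% | 14.1% | 9.9% | 0.10 |
| 50% | 22.3% | 9.9% | 0.20 |
| 30% | 34.8% | 9.9% | 0.33 |

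A generalised least squares check on 25 one-lesion and 10 two-lesion patients gives similar widths (11.5-12.0%, 13.2-14.2%, 20.1-22.5%, 30.7-35.0%).

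If the SD of the differences stays at 15% but the slope is not 1, the residual SD falls and the intercept CI can be narrower than Table 4: 8.5% at CV 150% and slope 0.93 (s = 2.68), or 8.4% at CV 100% and slope 0.88 (s = 2.25).

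**Regression direction.** Take histopathology as error-free and vascuCAP as unbiased with SD 3.75. Regressing vascuCAP on histopathology gives an expected slope of 1. The equation as printed gives SDref²/(SDref² + SD²):

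- CV 150%: 1406.25/(1406.25 + 14.06) = 0.99
- CV 100%: 0.98
- CV 50%: 0.92
- CV 30%: 56.25/(56.25 + 14.06) = 0.80

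At CV 30% the expected slope CI at n=35 is about 0.67-0.93, which excludes 1 although no bias exists. At the three larger CVs the expected CI still covers 1 at this SD.

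**The case against.** **The n=35 widths may be read from the tables, not computed.** The text points to Tables 4 and 5, which have no n=35 column. Midpoints of the printed n=30 and n=40 entries, as a share of 25 mm³, are 9.96% and 13.32% for bias and 7.84% and 10.48% for precision. Rounded up, these are exactly 10, 14, 8 and 11. A reader might infer that three of the four quoted widths are separate errors; the documents do not support that. The 14% is consistent with rounding up either the midpoint or the formula value of 13.2%. The 8% is reachable by rounding up 7.2%. Only 11% fails against the formula (9.6%) under any rounding, and the two precision figures largely inherit the Table 5 fault. This part of the objection stands.

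**Average bias is a legitimate planning quantity.** The plan treats bias as a difference in its plots, bias profile and covariate regressions, and the fitted bias at the mean volume has a width close to Table 4's. That also stands, and it narrows the gap to a missing sentence that plans the CI for d-bar. It does not supply widths for the two intervals that carry the bias rules.

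**Sizing is partly deferred.** The spread of histopathology volumes will be known only after phase one, when the final number is set. This is fair, but the minimum of 35 is justified now.

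**The equation looks like a label swap.** Probably so. The words are explicit, which makes the correction easy, but as printed the two cannot both be followed.

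**Conclusion.** Three corrections are warranted.

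1. Table 5 is wrong against its own footnote throughout, by about 6-11% in interval length. The n=35 precision lengths should read about 7% and 10%.
2. The interval sized in Table 4 has no counterpart in the planned analysis, and the intervals that declare bias have no stated width.
3. The words and equation of the regression conflict, and the literal equation can signal proportional bias for an unbiased device. The size of that effect rests on error-free histopathology, SD 15% and the assumed CV.

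Two stronger readings do not hold. One is that 35 patients are too few: the Table 5 error overstates the widths, so n=35 does slightly better than quoted for the SD and about as quoted for the mean difference. The other is that the intercept CI must be wider than Table 4. That is so at slope 1 (about 12-35% against 9.9%), but slopes away from 1 can make it narrower, and the plan gives neither the slope nor the spread.

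The arithmetic in Tables 4 and 5 needs no assumption beyond the plan's own. The intercept, slope and direction figures are illustrations over an assumed range.

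**What to change.** In section 8.1:

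- Recompute Table 5 with m−1 df at both limits and restate the n=35 precision lengths as about 7% and 10%. Optionally give the bias width at SD 20% as about 13%.
- Add d-bar with a patient-clustered 95% CI as the estimate of average bias that Table 4 sizes, and state that Table 4 does not give the width of the intercept or slope CI.
- Correct the equation to match its words, with vascuCAP regressed on histopathology.

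The cost is one recomputed table, a few sentences and one added estimate with its interval. No extra patients are needed.

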**Table 4: Width of 95% CIs for Bias Based on Total Sample Size (n)\***

	n=10	n=20	n=30	n=40	n=50	n=60
SD=2.5 (10%)	$\pm 1.72$	$\pm 1.12$	$\pm 0.90$	$\pm 0.77$	$\pm 0.68$	$\pm 0.62$
SD=3.75 (15%)	$\pm 2.58$	$\pm 1.69$	$\pm 1.34$	$\pm 1.15$	$\pm 1.02$	$\pm 0.93$
SD=5.0 (20%)	$\pm 3.44$	$\pm 2.25$	$\pm 1.79$	$\pm 1.54$	$\pm 1.37$	$\pm 1.24$

\*The effective sample size,  $m$ , is calculated as  $m=(3/4)n+(1/4)n(2/[1+(s-1)0.5])$ , where  $s=2$ .

Then the half-width of the 95% CI for bias is  $t_{(m-1),\frac{\alpha}{2}} (SD/\sqrt{m})$ .

**Table 5: Estimated 95% CIs for SD Based on Total Sample Size (n)\***

	n=10	n=20	n=30	n=40	n=50	n=60
SD=2.5	[1.80,4.77]	[1.98,3.81]	[2.08,3.51]	[2.11,3.29]	[2.16,3.20]	[2.19,3.14]
SD=3.75	[2.70,7.16]	[2.97,5.71]	[3.11,5.26]	[3.17,4.94]	[3.24,4.80]	[3.29,4.71]
SD=5.0	[3.60,9.54]	[3.96,7.61]	[4.15,7.02]	[4.22,6.59]	[4.31,6.40]	[4.38,6.29]

\*The effective sample size,  $m$ , is calculated as  $m=(3/4)n+(1/4)n(2/[1+(s-1)0.5])$ , where  $s=2$ .

Then the 95% CI for the SD is  $[\sqrt{\frac{(m-1)s^2}{\chi_{\frac{\alpha}{2},(m-1)}^2}}, \sqrt{\frac{(m-1)s^2}{\chi_{(1-\frac{\alpha}{2}), (m-1)}^2}}]$ .

For degree and uniformity measurements for each analyte for each site (i.e. neck and leg), we will tabulate the histopathology value vs. the vascuCAP™ value. Any analyte not measurable will also be indicated in the table. In the distributions in the tables are similar, then the data from the two sites will be pooled.

The coverage probability (CP) will be reported which is the probability that the absolute difference between the value measured by vascuCAP™ and the value measured by histology is less than  $d_0$ , i.e.  $\pi = \Pr(|Y - X| < d_0)$ . We will report the CP for values for  $d_0$  of 0 and 1. 95% CIs for the CP will be constructed using methods for clustered binary data [6].

For volume, degree, and uniformity of the six functional analytes, we will estimate the reproducibility of the measures at different institutions (two sites), and under different scanner models and field strengths (1.5 and 3.0) and with respect to ranges documented in the literature according to collected patient characteristics. Multiple variable linear and logistic regression models will be built, where the dependent variable is the difference between the measured functional analyte and the true value, and the independent variables are institution, scanner model, field strengths, and patient characteristics. We will test whether the independent variables in the model are predictors of bias using F-tests, and Wald tests, respectively.

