**Table 1: Analytes interrogated by vascuCAP™, understood as a multiplex assay**

Analyte	Description	Type and Units	Truth Standard
Lipid Core	Distinguished by presence of lipids, intermixed with extracellular matrix fibers, and/or necrotic tissue.	Expressed by burden in mm  and categorical variables for degree and uniformity using a 0/1/2 scale.	Histopathology considered as ground truth.
Fibrosis	Intimal presence of dense, homogeneous/organized collagen extracellular matrix with smooth muscle cells/fibroblasts embedded therein, but no appreciable lipid or necrotic tissue.	Expressed by volume in mm  and categorical variables for degree and uniformity using a 0/1/2 scale.	Histopathology considered as ground truth.
Intra-plaque hemorrhage	Presence of erythrocytes in the deeper regions of the plaque, with or without communication to the lumen or neovasculature.	Expressed by burden in mm  and confidence in %.	Histopathology considered as ground truth.
Inflammation	Accumulations of macrophages and lymphocytes in the deeper regions of the plaque that may bridge the neointima, and the media of the vessel	Expressed by burden in mm  and categorical variables for degree and uniformity using a 0/1/2 scale.	Histopathology considered as ground truth.
Vascular Leak	Composed of endothelial permeability, neovascularization, necrosis, and collagen breakdown.)	Expressed by distribution volume in mm  and categorical variables for degree and uniformity using a 0/1/2 scale.	Histopathology considered as ground truth.
Calcification	Intimal/medial presence of calcification with osteoblasts present therein, but	Expressed by burden in mm  and categorical variables for	Histopathology considered as

Analyte	Description	Type and Units	Truth Standard
	containing no appreciable lipid or necrotic tissue.	degree and uniformity using a 0/1/2 scale.	ground truth.
Remodeling Ratio	Calculated as the ratio of vessel area with plaque to reference vessel wall area without plaque	Expressed with value less than 1 for inward remodeling and greater than 1 for outward remodeling	Calculations from manual contour by radiologist as an imperfect(subjective) reference standard

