#### 3.2 Study Outcome Measures

Measured results will be compared in a blinded fashion with histology to assess performance of vascuCAP™-Profiling and build a prediction model in vascuCAP™-Scoring according to the following study endpoints:

- I. Measure the bias, precision, and reproducibility of each of the functional analytes as measured by vascuCAP™ with respect to histopathologic results as ground truth, and assess their linear region and limits of quantitation:
  - a. Plaque lipid core pool presence and volume.
  - b. Plaque fibrosis volume, degree, and uniformity.
  - c. Plaque inflammation burden, degree, and uniformity.
  - d. Intra-plaque hemorrhage burden and confidence.
  - e. Plaque vascular leak - volume, degree, and uniformity.
  - f. Calcification – volume, degree, and uniformity.
- II. Establish performance characteristics of the structural and hemodynamic analytes, where an objective truth standard is lacking:
  - a. Determine the interchangeability of structural measurements of wall thickness, remodeling ratio and luminal narrowing and hemodynamic measurements (ESS) with an imperfect (subjective) reference standard of manual contouring by radiologists. vascuCAP™ will be evaluated under two scenarios: fully-automated vascuCAP™, and a workflow where a reader will have the opportunity to review and adjust vascuCAP™ produced results.
  - b. Assess the reproducibility under different clinical sites, scanner models, and field strengths (dependent variable of interest being the interchangeability for each analyte relative to the imperfect reference standard) and with respect to ranges documented in literature according to collected co-variates.
- III. Classify the target lesion according to whether the analytes suggest it is not a plaque, or if it is, which of the 8 AHA types best fits the analyte profile. Assess the accuracy of vascuCAP™'s classification against the histopathology classification.

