### 8.1 Aim I

The first study aim is to estimate the bias and precision of each of the following functional analytes, which will be measured for each target lesion by both vascuCAP™ and histopathology:

- a. Plaque lipid
- b. Plaque fibrosis
- c. Plaque inflammation
- d. Intra-plaque hemorrhage burden and confidence.
- e. Plaque vascular leak
- f. Calcification

For each of these functional analytes, three measurements will be evaluated for a total of 18 measurements per target lesion: volume in mm^3, and degree and uniformity both measured on a three-point ordinal scale. The same measurements will be taken via histopathology, where the volume of each analyte will be measured using the same units (i.e. mm^3); however, degree and uniformity are graded subjectively on histopathology by the pathologist.

We anticipate that each patient will have at least one target lesion and some patients, especially the PAD patients, will have two target lesions, on average. There will be no replicate measurements (i.e. all of the measurements are obtained objectively by the algorithm so multiple runs should not produce different results).

For volume measurements for each analyte for each site (i.e. neck and leg), we will plot the value measured by histopathology vs. the difference between the value measured by vascuCAP™ and the value measured by histopathology. Any analyte not measurable will also be indicated on the plot using a different plotting character. The resulting plot will be inspected visually for the following:

1. Limits of vascuCAP™'s quantitation;
2. Associations between the magnitude of the histopathology measurement and bias; and
3. Associations between the magnitude of the histopathology measurements and heteroscedasticity in the vascuCAP™ measurements.

If the plots of carotid and femoral endarterectomies have similar distributions, then the data from these sites will be pooled; otherwise, separate analyses will be performed.

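### For degree and uniformity, the coverage probability is defined with a strict inequality at d0 = 0 and 1, so one result is always 0 and within-one-grade agreement gets no confidence interval

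*Combined protocol and SAP*

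**What the plan says.** Section 8.1 describes the ordinal part of Aim I as "degree and uniformity both measured on a three-point ordinal scale". Table 1 gives the codes: "categorical variables for degree and uniformity using a 0/1/2 scale".

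The text after Table 5 plans three things for these measures:

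- **Cross-table.** For each analyte and anatomic site, "we will tabulate the histopathology value vs. the" vascuCAP value, with neck and leg pooled if their distributions look similar.
- **Coverage probability.** This is the probability that "the absolute difference between the value measured by vascuCAP™ and the value measured by histology is less than" d0, and the formula repeats the strict sign: π = Pr(|Y − X| < d0). Then: "We will report the CP for values for $d_0$ of 0 and 1". The 95% CIs are to use methods for clustered binary data.
- **Reproducibility regression.** Linear and logistic models "where the dependent variable is the difference between the measured functional analyte and the true value", with institution, scanner model, field strength and patient characteristics as predictors.

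Earlier in Section 8.1 the same strict definition is used for volumes, where the CP is plotted over a range of d0.

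**The concern.** The volume definition appears to have been carried over to a three-point scale. On a continuous scale, < and ≤ give the same probability. On a scale where the difference takes only three integer values, they give different quantities, and the two chosen thresholds fall exactly on those values.

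The CP is the only agreement statistic with a planned CI for degree and uniformity. These measures belong to primary objective I, and Section 4 sends the phase-two results for Aims I and II into the 510(k) filing. The regression looks for predictors of bias and does not estimate agreement.

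An analyst who follows the text reports a column of zeros, plus a CP(1) that a reader may take for agreement within one grade. An analyst who changes < to ≤ without saying so departs from the written definition. The plan should settle which quantity is meant before the phase-two data are analysed.

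**Working it through.** The plan gives no expected agreement and no numerical CP for degree or uniformity, so there is no stated figure to reproduce. The check is an enumeration, followed by a count of the outputs affected and an illustration of precision.

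**1. Enumeration.** X and Y each take the values 0, 1, 2, giving 3 × 3 = 9 grade pairs. Of these, 3 have |Y − X| = 0, 4 have |Y − X| = 1, and 2 have |Y − X| = 2.

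| d0 | Cells with \|Y − X\| < d0 (as written) | Cells with \|Y − X\| ≤ d0 |
|---|---|---|
| 0 | 0 of 9 (empty) | 3 of 9 (exact) |
| 1 | 3 of 9 (exact) | 7 of 9 (within one grade) |
| 2 | 7 of 9 (within one grade) | 9 of 9 |

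As written, CP(0) = Pr(|Y − X| < 0) = 0 whatever the data, and CP(1) = Pr(Y = X). Within-one-grade agreement would need ≤ at d0 = 1 or < at d0 = 2, and neither is planned.

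**2. The CI for CP(0).** Take the phase-two minimum: 25 carotid patients with one lesion and 10 PAD patients with two, so 25 + 20 = 45 lesions. The estimate is 0/45 and every patient-level residual is 0. Both the clustered ratio variance and the binomial variance p(1 − p)/45 are therefore 0, and the interval carries no information.

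**3. Effect on a report.** Take an invented table of 90 lesions with 67 exact, 20 off by one grade and 3 off by two.

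- As written: CP(0) = 0 and CP(1) = 67/90 = 0.744.
- With ≤ at 0 and 1, or < at 1 and 2: 67/90 = 0.744 and 87/90 = 0.967.

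**4. How many measurements.** The sections differ on which analytes carry degree and uniformity.

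- Section 8.1: all six analytes, 6 × 2 = 12.
- Table 1: five analytes (hemorrhage has burden and a confidence percentage), 5 × 2 = 10.
- Section 3.2: four analytes, since lipid is "Plaque lipid core pool presence and volume" and hemorrhage is "Intra-plaque hemorrhage burden and confidence", 4 × 2 = 8.

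Each measurement yields one constant-zero result, or two if neck and leg are not pooled (16 to 24 in all).

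**5. Precision of the omitted estimate (illustration).** The footnote to Tables 4 and 5 gives m = (3/4)n + (1/4)n(2/[1 + (s − 1)0.5]) with s = 2. At n = 35, m = 26.25 + 8.75 × 1.333 = 37.9. At n = 75, the upper figure for phase two in Section 4, m = 56.25 + 18.75 × 1.333 = 81.25. The Wilson 95% interval is

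[p + z²/(2m) ± z√(p(1 − p)/m + z²/(4m²))] / (1 + z²/m), with z = 1.96.

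| Assumed within-one-grade agreement | n = 35 (m = 37.9) | Width (points) | n = 75 (m = 81.25) | Width (points) |
|---|---|---|---|---|
| 80% | 64.8–89.7% | 25 | 70.0–87.3% | 17 |
| 90% | 76.5–96.1% | 20 | 81.6–94.8% | 13 |
| 95% | 83.1–98.7% | 16 | 87.9–98.0% | 10 |

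The agreement levels are assumptions. The within-patient correlation of 0.5 is stated for volumes and borrowed here for grades. Wilson on an effective size stands in for the planned clustered-binary method.

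**The case against.** The strongest reply is that this is a drafting slip with little effect. Thresholds of 0 and 1 on a three-grade scale make sense only as exact and within-one-grade agreement, so ≤ was probably meant, and a result of 0 everywhere would expose the error when it is first programmed. The cross-table still gives the within-one-grade proportion, and exact agreement, the more demanding measure, keeps its estimate and CI under the label CP(1). Within-one-grade agreement is a lenient statistic here: it excludes only 0-versus-2 disagreements, and two independent raters with uniform grades would reach 7/9 = 78%. Section 8.1 calls the volumes the most critical measurements, and they are untouched. No acceptance criterion is attached to these CPs.

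Most of this stands as a limit on weight. Two points in it also qualify the figures above. The interval widths show how precise the omitted estimate would be, not the size of the error, and similar imprecision would remain after correction. The counts repeat one slip across outputs.

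It does not remove the problem. That ≤ was intended is an inference, because the strict inequality appears in both words and symbol and nothing elsewhere in the document corrects it. The cross-table supplies a point estimate without a CI that allows for patients contributing two lesions. The leniency of within-one-grade agreement is a reason to label it clearly and report it beside exact agreement.

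**Conclusion.** The concern holds. Followed as written, one of the two CPs planned for every degree and uniformity measurement is 0 for any data, the other is exact agreement, and within-one-grade agreement has neither a CP nor a clustered CI. This follows from the 0/1/2 scale and the strict inequality alone and needs no assumption about the data.

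It touches 8, 10 or 12 measurements according to the section read. The illustrative intervals rest on the assumptions given with them; they show only that the within-one-grade estimate should not be read without its CI at these sample sizes. The consequences are bounded: a misreading of CP(1) can only understate the device's performance, and the volume analysis and the sample-size reasoning do not change. It should be corrected because it is a stated rule for a primary aim that returns an empty result.

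**What to change.** In the degree and uniformity paragraph of Section 8.1, and for the ordinal measures only, define the CP as Pr(|Y − X| ≤ d0) in both the words and the formula, with d0 = 0 and 1. Equivalently, keep the strict sign and set d0 to 1 and 2. Label the two results exact agreement and agreement within one grade, and state that each has a 95% CI by the clustered-binary method. Leave the volume definition as it is.

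The cost is one paragraph of text, with no new data and no change to sample size. The same paragraph cites reference 6 for the clustered-binary method, but that entry concerns tissue classification. The volume text cites reference 14, which is the clustered-binary paper, so the citation can be corrected in the same edit.
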